#### 7.1.1.4 Dosing and Administration

Prior to the IP infusion, Investigators must determine whether there is a clinically significant infection. In case of infection, the IP infusion will be delayed until the infection resolves.

Premedication with a corticosteroid (eg, methylprednisolone 100 mg IV or equivalent; equivalent methylprednisolone dose should be calculated using [Table 9](#) below) will be administered

approximately 30-60 minutes prior to each inebilizumab infusion, and an antihistamine (eg, diphenhydramine 25-50 mg orally or equivalent) and an anti-pyretic (eg, acetaminophen 500-650 mg orally or equivalent) will be administered approximately 30-60 minutes prior to each IP infusion. Sites should use local supplies of these premedications.

**Table 9 Predose IV Corticosteroid Dose Conversion**

Corticosteroid (IV)	Equivalent glucocorticoid dose (mg)
Methylprednisolone	100
Triamcinolone	100
Prednisolone	125
Hydrocortisone	500
Dexamethasone	18.8*
Betamethasone	18.8*

IV = intravenous.

The table shows equivalence to a dose of IV methylprednisolone. For example, 125 mg of IV prednisolone is equivalent to 100 mg of IV methylprednisolone.

\*Dose can be rounded to the nearest vial for ease of use (ie, 20 mg).

Vital signs will be obtained prior to the start of each IP infusion. An experienced and qualified staff member will place the IV access.

Prior to the start of the infusion, please be sure that the bag content is at room temperature to avoid an infusion reaction due to the administration of the solution at low temperatures. The prepared solution will be IV administered via an infusion pump at an increasing rate over approximately 90 minutes through an IV line containing a sterile, low-protein binding 0.2 or 0.22 micron in-line filter according to the schedule in [Table 10](#).

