## 7.2 Additional Study Medications

### 7.2.1 Oral Corticosteroid Taper

Subjects who enter the study receiving oral corticosteroids will continue to receive oral corticosteroids at the time of randomization ([Section 4.1](#)).

Corticosteroids may only be used in the following circumstances:

1. The subject was on corticosteroids at the time of randomization and is using corticosteroids per protocol, or
2. For short-term use of non-MG medical conditions (eg, asthma exacerbation) when approved by the medical monitor.

**Initial Corticosteroid Dose at Randomization:** Subjects entering the study may or may not already be receiving a corticosteroid. Subjects who are already receiving a corticosteroid at the time of randomization will continue to receive a corticosteroid. Subjects who are not already receiving a corticosteroid at time of randomization will not start corticosteroid treatment.

Prednisone will be used as the preferred oral corticosteroid, to be provided to the subject as part of study procedures. Prednisolone is an allowed alternative to prednisone and should be used at the same dose as prednisone. If prednisone or prednisolone are not available locally, an alternative oral corticosteroid can be used following discussion with the medical monitor and agreement on the correct prednisone equivalent dose.

Subjects may be receiving up to 40 mg prednisone daily or 80 mg every other day or an equivalent dose of an alternate corticosteroid. If a subject is on an alternate corticosteroid, the equivalent prednisone dose should be calculated using [Table 11](#). If a subject enters on a dose of prednisone (or equivalent) not shown in the table (eg, 35 mg prednisone daily), then the next lowest dose shown in the table should be used as the starting dose for that subject (30 mg prednisone daily in this example). Any subject on an every other day steroid regimen will be changed to an equivalent daily steroid regimen (eg, 40 mg every other day = 20 mg daily).

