**Table 11 Corticosteroid Dose Conversion**

Corticosteroid	Equivalent glucocorticoid dose (mg)
Prednisone	5
Prednisolone	5
Triamcinolone	4
Methylprednisolone	4
Dexamethasone	0.75
Betamethasone	0.6
Hydrocortisone	20

The table shows equivalence to a dose of prednisone. For example, 5 mg of prednisolone is equivalent to 5 mg of prednisone; 4 mg of methylprednisolone is equivalent to 5 mg of prednisone.

**RCP Corticosteroid Tapering Procedure:** Starting at the RCP Week 4 visit, all subjects who are on corticosteroids will undergo the protocol-specified corticosteroid taper shown in [Table 12](#). Tapering will occur until a subject is on prednisone 5 mg daily, at which time the subject will remain on that dose during the remainder of the RCP. A site may elect to use prednisone 10 mg every other day as an alternative to prednisone 5 mg daily. If a subject begins the study on a prednisone dose that is  $\leq 5$  mg daily but  $> 0$  mg, then the subject should continue on that dose without tapering during the RCP. To maximize compliance with the corticosteroid taper, sites are encouraged to remind subjects (eg, by a phone or an email reminder) of tapering timepoints that do not align with a study visit (eg, RCP Week 16, RCP Week 20, and RCP Week 24). Any deviation from the corticosteroid tapering schedule should be reviewed with a study medical monitor.

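### Protocol Table 9 gives betamethasone 18.8 mg as equal to 100 mg IV methylprednisolone, but Table 11 implies 15 mg; the Table 9 cell is the likelier error

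*Protocol*

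**What the plan says.** Section 7.1.1.4 of the protocol calls for a steroid premedication, with methylprednisolone 100 mg IV as the example, and sends sites to Table 9 to work out the dose of a substitute. It adds "Sites should use local supplies of these premedications". Table 9 is anchored at "Methylprednisolone 100" mg and lists "Betamethasone 18.8" mg. The dexamethasone row directly above shows the same figure, and both rows carry an asterisk to a footnote allowing rounding to 20 mg.

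Table 11 in Section 7.2.1 converts oral steroids to prednisone. It lists dexamethasone at 0.75 mg and "Betamethasone 0.6" mg, and its note confirms the methylprednisolone link: "4 mg of methylprednisolone is equivalent to 5 mg of prednisone".

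The safeguards differ. For an alternative oral steroid used on study, Section 7.2.1 requires discussion with the medical monitor and "agreement on the correct prednisone equivalent dose". Section 7.1.1.4 and Table 9 state no such check for the premedication.

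**The concern.** Both tables state glucocorticoid equivalence, and both include methylprednisolone, so each can be rescaled to the other. Table 11 treats betamethasone as more potent than dexamethasone (0.6 mg against 0.75 mg for the same effect), while Table 9 treats them as equal. Both cannot be right.

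What is at stake depends on which table is wrong:

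- **Table 9 wrong.** A site that follows the protocol exactly and uses betamethasone gives more than the intended 100 mg methylprednisolone equivalent. This can recur at each infusion: Days 1 and 15 of the randomized controlled period, Day 183 as well for AChR-Ab+ subjects, and up to seven open-label infusions. No eligibility, stratum or taper decision changes.
- **Table 11 wrong.** Oral betamethasone doses convert to prednisone equivalents that are 25% too high. That can move a subject across the 5 mg/day stratum boundary (used outside Japan only), into a different starting row of the Table 12 taper, or over the 40 mg/day entry ceiling.

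**Working it through.** **Inputs.** Table 11, per 5 mg prednisone: methylprednisolone 4 mg, triamcinolone 4 mg, prednisolone 5 mg, hydrocortisone 20 mg, dexamethasone 0.75 mg, betamethasone 0.6 mg. Table 9, per 100 mg methylprednisolone: the doses listed in Step 2.

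**Step 1: scale factor.** 100 ÷ 4 = 25.

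**Step 2: apply it to every shared row.**

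- Methylprednisolone: 4 × 25 = 100 mg; Table 9 prints 100 mg.
- Triamcinolone: 4 × 25 = 100 mg; Table 9 prints 100 mg.
- Prednisolone: 5 × 25 = 125 mg; Table 9 prints 125 mg.
- Hydrocortisone: 20 × 25 = 500 mg; Table 9 prints 500 mg.
- Dexamethasone: 0.75 × 25 = 18.75 mg; Table 9 prints 18.8 mg (rounding).
- Betamethasone: 0.6 × 25 = 15.0 mg; Table 9 prints 18.8 mg.

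Five of six rows reproduce, counting the methylprednisolone anchor. Betamethasone alone does not.

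**Step 3: size of the gap if Table 9 is wrong.**

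- Printed dose: 18.8 ÷ 15 = 1.253, about 25% high. In methylprednisolone terms by Table 11, 18.8 × 4 ÷ 0.6 = 125.3 mg instead of 100 mg.
- Rounded dose: 20 ÷ 15 = 1.333, or 33% high; 20 × 4 ÷ 0.6 = 133.3 mg.
- For dexamethasone, the same rounding adds only 20 ÷ 18.75 = 1.067, or 6.7%.

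**Step 4: other explanations.**

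- *Route (IV against oral):* the other drugs convert between the tables with no further factor, so route does not account for it.
- *Vial rounding:* the 18.8 mg figure is already 25% high before any rounding.
- *Repeated cell:* 18.8 ÷ 25 = 0.752, which is Table 11's dexamethasone value, not its betamethasone value.

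**Step 5: the alternative, Table 11 wrong.** If the Table 11 entry should be 0.75 mg, its prednisone equivalents are too high by 0.75 ÷ 0.6 = 1.25. Classification then changes only in these betamethasone ranges:

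- Stratum (prednisone above 5 mg/day): the cut is 0.60 mg/day betamethasone by the current table and 0.75 mg/day by the alternative, so doses above 0.60 mg and up to 0.75 mg/day are affected.
- 7.5 mg taper row: it starts at 0.90 mg/day by the current table and at 1.125 mg/day by the alternative, so doses from 0.90 mg to below 1.125 mg/day are affected.
- Entry ceiling (prednisone 40 mg/day): it is 4.8 mg/day by the current table and 6.0 mg/day by the alternative, so doses above 4.8 mg and up to 6.0 mg/day are affected.

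For example, 1 mg/day is 1 × 5 ÷ 0.6 = 8.3 mg prednisone by the current table and 1 × 5 ÷ 0.75 = 6.7 mg by the alternative. Section 7.2.1 says that for a dose not listed, "then the next lowest dose shown in the table should be used as the starting dose for that subject". Under that rule the first value starts in the 7.5 mg row and the second in the no-taper row. Higher taper rows shift in the same way. At 0.7 mg/day (5.83 mg against 4.67 mg) the stratum changes but neither value leads to a taper; the starting dose would be 5 mg against 4.67 mg.

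**The case against.** The strongest objection is about direction. The documents show a disagreement, not an overdose. Neither table cites a source, and the case against Table 9 rests on its cell matching the dexamethasone cell. Betamethasone carries its own asterisk, so an author may have treated the two drugs as interchangeable for a single IV dose. This stands as a limit on certainty: the direction is an inference. But Table 11 gives the two drugs different potencies, and Table 9 states no exception.

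Second, the weight is small:

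- The 33% arises only if a site uses the optional rounding.
- The 100 mg is given as an example, and the excess is about 25 to 33 mg methylprednisolone equivalent on isolated infusion days, in subjects who may already take up to 40 mg prednisone daily.
- Section 2.1.4 says all subjects receive the prophylaxis, and the product is blinded, so no route to bias between arms is visible.
- The documents do not say whether any site uses betamethasone.

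All of this stands and is why the point is minor.

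Third, the Table 11 branch is remote. Prednisone is the preferred, study-supplied oral steroid, and an alternative needs the medical monitor's agreement. The no-taper reading of 6.7 mg also depends on the next-lowest-dose rule, whereas Section 4.1 says that anyone entering above 5 mg/day is tapered. This is fair, and the ranges in Step 5 should be read as bounds on a less likely case.

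None of this removes the contradiction. One of two operative conversion tables prints a wrong dose, and the one more likely to be wrong has no stated check on its use.

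**Conclusion.** The concern holds as a minor point. Tables 9 and 11 cannot both be right for betamethasone: 18.8 mg is printed where Table 11 gives 15 mg. This rests on the protocol's own figures and is certain. That Table 9 is the wrong one is the likelier reading, not a proven one.

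On that reading, betamethasone premedication is 25% too high as printed and 33% too high if rounded to 20 mg, and no trial classification is affected. If Table 11 is wrong instead, the error is a 25% overstatement of prednisone equivalents, which matters only within the narrow oral betamethasone ranges shown. Either way the primary analysis, power and type I error are untouched. The practical effect depends on betamethasone being used at all, which the documents do not tell us.

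**What to change.** Check the reference from which the tables were built, then correct one of them:

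- If it supports 0.6 mg per 4 mg methylprednisolone, change the betamethasone cell in Table 9 to 15 mg and remove the 20 mg rounding footnote from that row.
- If it supports 18.8 mg per 100 mg methylprednisolone, change the betamethasone entry in Table 11 to 0.75 mg.

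Then notify sites of the corrected value. The cost is one table cell at the next amendment (with its footnote marker, if the cell is in Table 9) and a short site or pharmacy memo.

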**Table 10 Infusion Rate for Investigational Product After Dilution in a ■■■ mL Intravenous Bag**

Elapsed Time (minutes)	Recommended Infusion Rate (mL/hour)
0 to 30	42
31 to 60	125
61 to end of infusion	333

If an infusion reaction occurs, the site should slow or, if this does not help, stop the infusion. Resumption of the infusion is at the discretion of the site qualified personnel. Unless an infusion reaction occurs resulting in discontinuation of the infusion, the entire infusion bag contents must be administered, and the tubing must be flushed with a volume of saline at least as large as that of the tubing to ensure complete delivery of the IP. When flushing the tubing, the infusion rate should not exceed 333 mL/hour.

After the completion of the infusion, subjects will be observed for at least one hour.

Medically qualified personnel must be immediately available to respond to emergencies during administration of the IP. Appropriate drugs and medical equipment to treat acute hypotensive, bronchoconstrictive, or anaphylactic reactions must be immediately available, and study personnel must be trained to recognize and treat these reactions. Additionally, appropriate drugs

and medical equipment to treat IRRs must be immediately available, and study personnel must be trained to recognize and treat IRRs.

**Duration of Administration** is defined as the amount of time elapsed from the infusion pump start time to the infusion pump stop time plus the time required to clear the infusion line of residual IP. The duration of administration will be recorded in the eCRF.

#### 7.1.1.5 Investigational Product Accountability

Study site staff will maintain a record of the IP doses received, dispensed, administered, and destroyed. All records will be maintained with controlled access. The Investigator will administer the IP only to subjects included in this study and according to the procedures established in this study protocol. Each administration of the IP will be documented and transferred to the eCRF.

#### 7.1.1.6 Investigational Product Handling and Disposal

The Investigator or designee must return any unused IP to the Sponsor or designee regardless of whether the study was completed or terminated prematurely. At the time of return, the Investigator must verify that unused or partially used IPs have been returned and that no IPs remain at the site. As an alternative to returning unused IPs at the end of the study, the Investigator may destroy unused IPs on site with agreement from the Sponsor.

### 7.1.2 Monitoring of Dose Administration

Vital signs (body temperature, BP, pulse rate, and respiratory rate) must be taken with the subject in a seated position as follows:

- Within 60 minutes prior to administration of the IP
- 15 ( $\pm$  5) minutes after the start of the infusion and then every 30 ( $\pm$  10) minutes until completion of infusion
- At the completion of infusion ( $\pm$  10 minutes)
- 60 ( $\pm$  10) minutes after dosing (repeated as needed until stable)

If a hypersensitivity reaction occurs during the infusion, vital signs will be taken more frequently, as warranted by the severity of the reaction.

#### 7.1.3 Reporting Product Complaints

A product complaint is any written, electronic, or oral communication that alleges deficiencies related to the identity, quality, durability, reliability, safety, effectiveness, or performance of a drug, combination product, or device after it is released for distribution to market or clinic by either the Sponsor, distributors, or partners for whom the Sponsor manufactures the material. This includes all components distributed with the drug, such as packaging drug containers, delivery systems, labeling, and inserts.

Report product complaints to the Sponsor within one business day of discovery by completing the applicable product complaint form found in the Pharmacy Manual and submitting a copy as instructed via the Pharmacy Manual. Retain product unit(s) associated with the complaint in quarantine under labeled storage conditions until the Sponsor advises whether product should be

destroyed or returned be evaluated, or for a maximum of 45 calendar days after reporting the product complaint to Sponsor.

## 7.2 Additional Study Medications

### 7.2.1 Oral Corticosteroid Taper

Subjects who enter the study receiving oral corticosteroids will continue to receive oral corticosteroids at the time of randomization ([Section 4.1](#)).

Corticosteroids may only be used in the following circumstances:

1. The subject was on corticosteroids at the time of randomization and is using corticosteroids per protocol, or
2. For short-term use of non-MG medical conditions (eg, asthma exacerbation) when approved by the medical monitor.

**Initial Corticosteroid Dose at Randomization:** Subjects entering the study may or may not already be receiving a corticosteroid. Subjects who are already receiving a corticosteroid at the time of randomization will continue to receive a corticosteroid. Subjects who are not already receiving a corticosteroid at time of randomization will not start corticosteroid treatment.

Prednisone will be used as the preferred oral corticosteroid, to be provided to the subject as part of study procedures. Prednisolone is an allowed alternative to prednisone and should be used at the same dose as prednisone. If prednisone or prednisolone are not available locally, an alternative oral corticosteroid can be used following discussion with the medical monitor and agreement on the correct prednisone equivalent dose.

Subjects may be receiving up to 40 mg prednisone daily or 80 mg every other day or an equivalent dose of an alternate corticosteroid. If a subject is on an alternate corticosteroid, the equivalent prednisone dose should be calculated using [Table 11](#). If a subject enters on a dose of prednisone (or equivalent) not shown in the table (eg, 35 mg prednisone daily), then the next lowest dose shown in the table should be used as the starting dose for that subject (30 mg prednisone daily in this example). Any subject on an every other day steroid regimen will be changed to an equivalent daily steroid regimen (eg, 40 mg every other day = 20 mg daily).

**Table 11 Corticosteroid Dose Conversion**

Corticosteroid	Equivalent glucocorticoid dose (mg)
Prednisone	5
Prednisolone	5
Triamcinolone	4
Methylprednisolone	4
Dexamethasone	0.75
Betamethasone	0.6
Hydrocortisone	20

The table shows equivalence to a dose of prednisone. For example, 5 mg of prednisolone is equivalent to 5 mg of prednisone; 4 mg of methylprednisolone is equivalent to 5 mg of prednisone.

**RCP Corticosteroid Tapering Procedure:** Starting at the RCP Week 4 visit, all subjects who are on corticosteroids will undergo the protocol-specified corticosteroid taper shown in [Table 12](#). Tapering will occur until a subject is on prednisone 5 mg daily, at which time the subject will remain on that dose during the remainder of the RCP. A site may elect to use prednisone 10 mg every other day as an alternative to prednisone 5 mg daily. If a subject begins the study on a prednisone dose that is  $\leq 5$  mg daily but  $> 0$  mg, then the subject should continue on that dose without tapering during the RCP. To maximize compliance with the corticosteroid taper, sites are encouraged to remind subjects (eg, by a phone or an email reminder) of tapering timepoints that do not align with a study visit (eg, RCP Week 16, RCP Week 20, and RCP Week 24). Any deviation from the corticosteroid tapering schedule should be reviewed with a study medical monitor.

**Table 12 Randomized Controlled Period Prednisone Tapering Schedule**

RCP Baseline dose (Day 1) (mg/day)	RCP Week 4 dose (Day 29) (mg/day)	RCP Week 8 dose (Day 57) (mg/day)	RCP Week 12 dose (Day 85) (mg/day)	RCP Week 16 dose (Day 113) (mg/day)	RCP Week 20 dose (Day 141) (mg/day)	RCP Week 24 dose through end of RCP (Day 169) (mg/day)
40	30	20	15	10	7.5	5
30	20	15	10	7.5	5	5
20	15	10	7.5	5	5	5
15	10	7.5	5	5	5	5
10	7.5	5	5	5	5	5
7.5	5	5	5	5	5	5
$\leq 5$	No taper					

RCP = randomized controlled period.

**OLP Corticosteroid Tapering:** Subjects who are receiving corticosteroids at the time of OLP entry can remain on prednisone 5 mg daily or the dose can be tapered further at the discretion of the Investigator. If a dose of prednisone  $> 10$  mg daily is used for more than 8 consecutive weeks in the OLP, the IP must be discontinued. The rationale for this requirement is to reduce the potential risk of adverse effects associated with long-term use of moderate- or high-dose corticosteroids.

## 7.2.2 Rescue Medications

Worsening of symptoms in MG can occur due to precipitating factors that include disease progression, infection, tapering of therapies, or certain medications ([Wendell and Levine, 2011](#)). This worsening can range from mild to severe. Rescue therapy can be used in any of the following circumstances:

1. QMG score is  $\geq 4$  points higher than the baseline score, or
2. QMG score increases  $\geq 4$  points between study visits, or
3. The Investigator is concerned that the subject's health is in jeopardy (eg, significant worsening of bulbar function).

The protocol-allowed rescue therapy options include IVIg or PLEX. Intravenous Ig is recommended over PLEX for subjects in this study since PLEX may remove the IP from circulation, thus potentially decreasing its therapeutic effect (Khatrī et al, 2009). Subjects who are treated with a protocol-allowed rescue therapy can continue in the study. High-dose corticosteroids are not a protocol-allowed form of rescue therapy (eg, IV methylprednisolone).

Rescue therapies should be recorded on the study's rescue therapy dedicated eCRF pages.

Rescue therapy is considered standard of care treatment; information about Sponsor coverage of out-of-pocket costs incurred by subjects treated with rescue therapy will be included in the site contract.

### **7.3 Treatment Assignment and Bias Minimization**

#### **7.3.1 Treatment Allocation**

Acetylcholine receptor antibody positive (AChR-Ab+) and MuSK-Ab+ subjects will be randomized in a 1:1 ratio to receive inebilizumab or placebo.

The IP will be administered on Day 1 after randomization. If there is a delay in the administration of the IP such that it will not be administered within the specified timeframe, the site monitor must be notified immediately.

#### **7.3.2 Randomization Strategy and Procedure**

An interactive voice/web response system (IXRS) will be used for randomization to a treatment group and assignment of IP kit numbers. Subjects will be enrolled into either the AChR-Ab+ or MuSK-Ab+ population. Within each population, subjects will be stratified by region first (non-Japan vs Japan). In the non-Japan population, subjects will be further stratified according to baseline disease severity ("Day 1 QMG score = 11-15" vs "Day 1 QMG score  $\geq 16$ ") and baseline corticosteroid use ("prednisone  $> 5$  mg/day" vs "prednisone  $\leq 5$  mg/day") and randomized 1:1 to receive either inebilizumab or placebo within each stratum. In the Japan population, no further stratification will be applied due to the small sample size, and subjects will be randomized 1:1 to receive either IV inebilizumab or placebo.

A subject is considered randomized into the study when the Investigator notifies the IXRS that the subject meets eligibility criteria and the IXRS provides the assignment of treatment group and allocates treatment, including IP kit number.

Additional details are provided in the IXRS Manual.

